Tumor imaging evaluation	√	√	√	If the subject has no progression of disease when withdrawal from the study, the tumor still has to be evaluated once every 6 weeks according to RECIST v1.1, until progression of disease or start of subsequent anti-cancer therapy. Including the enhanced CT scan at thorax, abdomen, pelvis and site of lesions. In case of allergy to the contrast agent for enhanced CT scan, thoracic plain CT scan + abdominal and pelvic MRI can be performed. Bone scan is only performed when clinically indicated.

Items	End-of-Treatment ^[5]	Follow-up period		Comment
		Safety follow-up ^[6]	Survival follow-up ^[7]	
Others				
Survival information		√	√	
Subsequent anti-cancer therapy		√	√	

Note: [1] All the baseline data will be based on the value closest to the study dose.

- [2] For the subjects who have failed screening and are enrolled during re-screening period, if the visit procedures completed at the initial screening, and meet the required time limit for this procedure prior to start dose of the investigational drug and meet the inclusion criteria, they do not need to repeat the procedure during the re-screening period.
- [3] There's no ± 3 days window period for Day 1 of Cycle 1.
- [4] Starting from Cycle 2, the test will be performed on $D1 \pm 3$ of each cycle or at least once every 42 days, and more frequently when clinically indicated.
- [5] End of Study Treatment/Withdrawal from Study: If these tests/procedures have been completed within 7 days after withdrawal from the study, no further repetition is required.
- [6] Safety follow-up: until 90 days after last dose. During this period, one visit will be performed once every 30 days (± 7 days). The first (30 days after the last dose) and third (90 days after the last dose) safety visit after receiving drugs must be performed at the study center, the second visit (60 days after the last dose) is telephone visit, and only survival data, concomitant medication/therapy, AE need to be collected.
- [7] Survival follow-up: The subjects will enter the survival follow-up period after the end of safety follow-up period. During this period, the subjects will be followed up by telephone once every 30 days (± 7 days) for collection of survival data and subsequent therapies.

ABBREVIATIONS AND DEFINITIONS

The following abbreviations and special terms will be used in the study protocol.

Abbreviation and specific terms	Definition
AE	Adverse event
AFP	Alpha fetoprotein
ALP	Alkaline phosphatase

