3.2.3 Follow-up period

Follow up period is initiated when the end-of-treatment decision is made.

Within 90 days after the last dose of investigational drug, follow-up visit will be performed once every 30 days (± 7 days), the first and third follow-up must be face-to-face visit, and the required safety evaluation must be completed (see study flowchart), the second follow-up is telephone visit (only collect partial data).

After the end of the safety follow-up period, the subjects will enter survival follow-up period. Investigators must follow up subject's survival every 30 days (± 7 days), until death, lost to follow-up, termination of study by the sponsor. Investigators can inquire the subject, his/her family members or local physician via phone, collect subject's survival information (death and reason of death) and data on other tumor therapies after the end of study treatment. The data on each survival follow-up needs to be recorded in detail in the original medical record.

Subjects who end study treatment for toxicity or other reasons with no radiological progression observed still need to receive radiological evaluation according to the same frequency, until progression of disease or start of other anti-cancer therapy, the radiological evidence on PD should be obtained from such subjects as much as possible.

The subject withdrawing from study treatment should also continue the safety follow-up and survival follow-up as required by protocol. Adverse effects of the investigational drug may occur after end of treatment; safety follow-up should be conducted as far as possible. Survival is one primary endpoint in this study, the study center should do their best to obtain the survival follow-up information.

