 - After the use of cortisol for management of treatment-related AEs, the study medication is allowed to be delayed for > 6 weeks due to the need for dose tapering. Discussion with the sponsor must be made before resuming the dose. During the dose delay, the tumor assessment should continue as required by the protocol. Safety visits and laboratory tests should also be performed at the original frequency (at least once every 6 weeks, window period \pm 7 days) or more frequently when clinically indicated;
 - The dose delay for > 6 weeks due to non-related reasons must be discussed with the sponsor prior to resuming administration. During dose delay, the tumor evaluation should still proceed as required in the protocol. Safety visits and laboratory examinations should also be performed at the original frequency (at least once every 6 weeks, window period \pm 7 days), or more frequently when clinically indicated;
- Clinical AE, laboratory abnormality, or complications may bring major risk to subjects who continue taking the study medication, as judged by investigators.
- Progression of disease evaluated by investigators in accordance with RECIST v1.1 (unless the subject meets the criteria in Section 3.2.4).

Even though the study medication is terminated, subjects must continue to perform tumor evaluation as required in the protocol.

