8.3 Independent Tumor Imaging Evaluation

In order to provide objective, neutral and reproducible efficacy data except investigators' evaluation, the 3rd-party Independent Radiology Review Committee (IRC) will be set up for tumor response evaluation in this study.

All the images (including unscheduled scan, possibly including bone scan or brain scan) obtained from each center will be centrally reviewed by IRC, and tumor evaluation will be performed in accordance with RECIST v1.1. The central evaluated data will be used for analysis of ORR, TTP, DoR and DCR. The clinical decisions related with response evaluation will be based on investigator's evaluation.

The detailed procedures and standard for central evaluation will be defined in the additional "Radiology Manual for Study Center".

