4.1.4. Progression-free survival (PFS)

Defined as the period from the date of first dose to the first documentation of PD in accordance with RECIST 1.1 or death due to any reason, whichever comes first. If a subject still shows no PD or does not die at the end of study, this period will be censored. The rules for PFS censoring are as below:

- If there is no tumor assessment at baseline, the date of censoring is the date of the first dose of study treatment.
- If there is no tumor assessment after baseline, the date of censoring is the date of the first dose of study treatment.
- If no RECIST 1.1 progression or death is recorded, the date of censoring is the date of the last tumor assessment.
- If no radiological progression or death is recorded prior to initiation of subsequent therapy, the date of censoring is the date of the last tumor assessment prior to the subsequent therapy.
- If subjects miss 2 or more consecutive planned tumor assessments prior to progression or death (12 weeks within 12 months from the first dose of study treatment, 24 weeks after 12 months from taking first dose), the date of censoring will be the date of the last tumor assessment.

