5.4. Efficacy Analysis

The efficacy analysis will be performed separately by group and overall.

Efficacy analysis will be based on IRC-assessed data and investigator-assessed data, with the former as the primary analysis.

Based on the FAS, PPS, and ES, ORR and 95% CI will be calculated separately by group and overall. The CI will be calculated using the Clopper-Pearson method. In addition, the difference in ORR will be calculated between the two groups, and Wald method will be used to estimate the 95% CI of the difference, and the nominal P value will be calculated based on Pearson Chi-square test.

In addition, based on the FAS, Amit method will be used to analyze the discrepancy between IRC-assessed and investigator-assessed PD/non-PD, BOR, and CR/PR.

Based on the FAS and PPS, Kaplan-Meier method will be used to calculate the 6/9/12-month OS% and the corresponding 95% CIs will be calculated.

Based on the FAS, the secondary efficacy endpoint PFS (including the 6/9/12-month PFS rate), TTP, OS, and DoR will be analyzed using Kaplan-Meier method. TTR will be descriptively summarized. When applicable, the survival curve will be plotted by endpoints. For PFS, TTP, OS, and DoR, the hazard ratios between groups and their 95% CIs will be computed using the COX proportional hazards model and nominal P values will be calculated using the log-rank test.

For the secondary efficacy endpoint DCR, the same statistical method with ORR will be used for analysis based on the FAS, the PPS, and the ES.

The best overall response (BOR) will be summarized.

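### Off-treatment scans may end at investigator-assessed progression while the IRC reading is primary, so IRC-based TTP, and somewhat less PFS, is likely to lean upward by an unknown amount (minor)

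*Protocol*

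**What the plan says.** **How long imaging lasts after treatment.** The protocol's Study Procedures table for end of treatment and follow-up has subjects without progression "evaluated once every 6 weeks according to RECIST v1.1, until progression of disease or start of subsequent anti-cancer therapy". Section 3.2.3 says that such subjects "still need to receive radiological evaluation according to the same frequency, until progression of disease or start of other anti-cancer therapy". The last paragraph of 3.2.4 repeats this for subjects who leave because of toxicity. None of the three names the assessor.

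**Whose reading counts during the trial.** Protocol 8.3: "The clinical decisions related with response evaluation will be based on investigator's evaluation". Among the reasons for permanent discontinuation, 7.2.4 lists "Progression of disease evaluated by investigators in accordance with RECIST v1.1", unless the criteria in 3.2.4 for treatment beyond progression are met. Subjects treated beyond progression keep being scanned.

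**Whose reading counts in the analysis.** SAP 5.4: "Efficacy analysis will be based on IRC-assessed data and investigator-assessed data, with the former as the primary analysis". Protocol 8.3 assigns ORR, TTP, DoR and DCR to central review and does not list PFS.

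**Censoring.** For PFS, SAP 4.1.4 states: "If no RECIST 1.1 progression or death is recorded, the date of censoring is the date of the last tumor assessment". SAP 4.1.5 has the same rule for TTP and also censors deaths without progression at the last scan. For PFS a death is an event unless it follows new therapy or two or more missed assessments (12 weeks in year 1, 24 weeks later). SAP 4.1.2 (DoR) counts any death and has neither of those two rules.

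**Planned checks.** SAP 5.4 also plans investigator-based analyses and an Amit-method comparison of the two readings.

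**The concern.** The reader who can end the imaging is not the reader whose call defines the event. When the investigator sees progression, treatment stops and no further scan is clearly required. If the IRC has not called progression on those images, its record ends there without an event. These subjects leave the risk set because someone saw their tumour growing, so they are likely to have an earlier IRC progression than those who stay. Kaplan-Meier treats them as average.

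SAP section 3 plans no formal hypothesis testing. TTP and PFS will therefore be read largely as absolute figures, and a bias shared by two schedules of the same drug does not show in a comparison between them.

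**Working it through.** The documents state no figure on this point: no IRC/investigator discordance rate, no PFS or TTP assumption, and no share treated beyond progression. The mechanism comes from the text; every size below rests on assumed rates.

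**Step 1. One subject, three endpoints.** Investigator progression at a scan, no IRC progression on the same images, treatment stopped, no later scan:

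| Endpoint | Recorded in the IRC analysis |
|---|---|
| TTP (SAP 4.1.5) | Censored at that scan, even if death follows |
| PFS (SAP 4.1.4) | Censored at that scan, unless death comes before new therapy and before two missed assessments |
| DoR (SAP 4.1.2) | Event at death whenever it occurs; censored at the last scan only if no death is recorded |

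**Step 2. A case that can be done by hand (TTP).** From the protocol: scans at weeks 8, 14, 20 and 26. Assumed: exponential time to investigator progression with median 13 weeks, so S(t) = 2^(−t/13); a share d that the IRC calls one scan later; nobody treated beyond progression; deaths ignored.

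- S(20) = 0.344 and S(26) = 0.250.
- Probability of investigator progression: up to week 8, 1 − 2^(−8/13) = 0.3472; per later 6-week interval, 1 − 2^(−6/13) = 0.2738.
- Scanning until IRC progression: S(26) + d × [S(20) − S(26)].
- Scanning stopped: [1 − (1−d) × 0.3472] × [1 − (1−d) × 0.2738]³.
- d = 0.1: 0.250 + 0.1 × 0.094 = 0.259, against 0.6875 × 0.7536³ = 0.294. Gap 3.5 points.
- d = 0.3: 0.250 + 0.3 × 0.094 = 0.278, against 0.757 × 0.8083³ = 0.400. Gap 12.2 points.

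A simulation of 100,000 subjects per setting adds deaths (median survival after progression 35 weeks; half start new therapy). At 6 months, in %:

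| d | TTP, full scanning | TTP, stopped | PFS, full scanning | PFS, stopped |
|---|---|---|---|---|
| 10% | 26.2 | 29.3 | 22.7 | 25.4 |
| 30% | 28.8 | 40.1 | 24.6 | 34.1 |

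The PFS gap is smaller (9.5 against 11.3 points at 30%) because about 10% of the stopped subjects die early enough to count. This is a corner case: a short median, an IRC lag of exactly one scan, and nobody continuing. With half treated beyond progression, the PFS gap at 30% falls to 4.2 points. With an average IRC lag of two scans and nobody continuing, it is 6.1.

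**Step 3. A middle setting.** Assumed: median 4 months, 70% agreement at the same scan, otherwise IRC progression at a later scan, 30% treated beyond progression, 40% starting new therapy, median survival after progression 8 months. Week 36.5:

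| Endpoint | Full scanning | Stopped | Investigator PD as event |
|---|---|---|---|
| TTP | 0.330 | 0.395 | 0.295 |
| PFS | 0.311 | 0.375 | 0.291 |

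The gaps are 6.5 and 6.4 points. With 90% agreement, PFS is 0.285, 0.307 and 0.280, a gap of 2.2 points. The share of subjects affected is about 0.7 × 10% = 7% to 0.7 × 30% = 21%.

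**Step 4. The assumption that drives the size.** Steps 2 and 3 make the IRC call a short delay after a correct investigator call. Suppose instead that discordant calls are investigator over-calls and later IRC progression comes at the ordinary rate. With the same median, agreement and share continuing, a parallel simulation puts the TTP overstatement at 1.6 points at week 24.5 (5.2 under the delay model) and 2.3 at week 36.5 (7.0).

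**Step 5. Does the planned investigator curve already give a lower bound?** Not necessarily. If the IRC sometimes calls progression first, investigator times can be later than IRC times. In one simulated setting with the IRC earlier in 15–20% of subjects, the investigator curve was 0.307 at week 36.5 and the full-scan IRC curve 0.305. Counting investigator progression only where the IRC has none by the last scan can only move an event earlier, so that curve stays below full scanning (0.289 in the same setting).

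**The case against.** **Imaging may not stop.** Section 3.2.2 runs imaging to progression or the end of the study, whichever is later, and 7.2.4 says that tumour evaluation continues as the protocol requires after the drug is stopped. That scans uniformly end at investigator progression is therefore an inference that the documents do not settle. But 3.2.2 describes the treatment period, and 7.2.4 refers back to requirements that ask for nothing after progression. What stands is that the passages conflict.

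**The SAP already looks at both readings.** The investigator-based curve and the Amit analysis will show disagreement. In one simulation of the middle setting for TTP at week 36.5, the proposed curve (0.289) lay close to the investigator curve (0.278), and both lay below full scanning (0.315). The gain is therefore modest. It consists of a count of affected subjects and a bound that survives early IRC calls.

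**The proposed curve can be the worse one.** If discordant calls are over-calls, it falls about 8 points below full scanning, further off than the primary curve. This stands, and is why it should be shown as a bound and not as a correction.

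**Not all endpoints are hit alike.** A reader might infer that PFS, TTP and DoR are all censored at the investigator's call. SAP 4.1.2 does not support that for DoR, and 4.1.4 keeps some PFS deaths. IRC-primary PFS also rests only on the SAP's general sentence: protocol 8.3 omits PFS, and 11.3.2 speaks of evaluation by the investigators.

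**Conclusion.** The point holds in limited form. No passage clearly requires imaging until IRC progression, the SAP makes the IRC reading primary, and its rules censor discordant subjects at the last scan for TTP and, with the exception for early deaths, for PFS. The censoring is likely informative and the direction is upward. For DoR, an IRC progression that would have been seen is replaced by a later death, or stays unobserved in a subject still alive at the cut-off.

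The size is not known. With 10–30% discordance and 30% treated beyond progression, both assumed, TTP is overstated by about 1 to 7 percentage points at weeks 24–37. The bias lies near the bottom of that range if discordant calls are investigator over-calls, and reaches about 11 points only in the corner case of Step 2 with deaths included.

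A reader might infer that this threatens the trial's conclusion. It does not: TTP, PFS and DoR are secondary, and the effectiveness rule in SAP section 3 uses only ORR and the 6-month OS rate. Severity: minor.

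**What to change.** In SAP 5.4, add a sensitivity analysis of IRC-based TTP and PFS in which investigator-assessed progression counts as an event on its date when the IRC has recorded no progression by the last available scan. Report, by group and overall, how many subjects the primary IRC analysis censors for this reason. Present the result beside the primary IRC curve as a conservative lower bound. State explicitly whether PFS is IRC-primary.

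In the protocol, the passages on how long imaging continues (the follow-up table, 3.2.2, 3.2.3 and 7.2.4) must be reconciled, and the assessor whose progression call ends it should be named.

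The SAP change costs one extra curve and table per endpoint, from data already collected. The added figures will be slightly less favourable.

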1. STUDY BACKGROUND

1.1 Epidemiology and Current Treatment Status of Hepatocellular Carcinoma

Primary carcinoma of the liver is a common malignant tumor worldwide, with about 748,300 new cases per year according to the statistics in 2008, accounting for 6% of the new cases of all the cancers and ranking the fifth^{1,2}. Up to 695,900 persons die per year due to its very poor prognosis, thus it has become the third cause of cancer death. China is a high-risk area for liver carcinoma, the number of cases accounting for about 55% of the world, the number of deaths accounting for 50%; it is the second most common tumor follows lung cancer. The high incidence age is 35–45 years for liver carcinoma, male cases more than females, at the ratio of 2–5:1 for male to female. Male patients account for higher proportion in the area with higher incidence.

Hepatocellular carcinoma (HCC) is the most common type in primary carcinoma of liver and accounting for 90%. The main risk factors for HCC are infection with hepatitis B virus (HBV) and hepatitis C virus (HCV) infection, water pollution (blue-green algae toxins), alcoholism and aflatoxin. HCC mostly occurs based on hepatitis virus infection and liver cirrhosis, approximately 10–20 years after primary hepatic damage.

Most HCC are asymptomatic in the early stage, most patients have reached locally advanced stage or had distant metastasis when diagnosis. There is no standard therapeutic method for advanced HCC currently. Its clinical treatment is facing severe challenges. The survival time is usually 3–6 months in the patients with advanced HCC in our country, and no longer than one year worldwide, which is greatly related with the lack of effective systematic treatment in these patients. HCC is resistant to common chemotherapy, its therapeutic methods basically include surgery (hepatectomy, transplantation and palliative surgery), non-surgical therapy (local therapy, arterial chemoembolization, chemotherapy, radiotherapy, biotherapy and molecular targeted therapy) and other therapeutic methods (including participation in clinical studies).

1.2 Advances in the Treatment of Hepatocellular Carcinoma

1.2.1 Advances of targeted therapy in the treatment of hepatocellular carcinoma

In December 2007, sorafenib became the first drug approved by US FDA for the treatment of HCC, which is based on the result of significant survival benefits from SHARP trial, in which sorafenib increased progression-free survival (medians: 5.5 months and 2.8 months, respectively) by 73% and overall survival (medians: 10.7 months and 7.9 months, respectively) by 44% compared with placebo. Thus, it opened up a new era of targeted therapy for HCC. Sorafenib was approved for treatment of HCC in China in 2008, providing a new therapeutic option for numerous patients with HCC, however, its high cost (about 50,000 RMB per month for each patient) limits its further use.

In addition, a variety of multikinase inhibitors under development have been frustrated in the clinical study versus sorafenib: the phase III clinical trial of sunitinib (developed by Pfizer) versus sorafenib was terminated in advance in April 2010, because sunitinib did not improve the survival time compared with sorafenib, and the incidence of serious adverse events (SAE) in sunitinib group was higher than that in sorafenib group. The multikinase inhibitor ABT-869 (linifanib, developed by Abbott) has no advantage compared with sorafenib. The phase III clinical trial of ABT-869 was terminated according to the advice by the independent data monitoring committee. A clinical study with 731 patients showed that the epidermal growth factor receptor (EGFR) tyrosine kinase inhibitor erlotinib (Tarceva, developed by Roche) faced failure for no increase of additional benefit as compared with sorafenib. Brivanib is a tyrosine kinase inhibitor targeted VEGF receptor and basic fibroblast growth factor (bFGF, FGF-2) receptor, in the phase II clinical trial in patients with advanced HCC who are unsuitable for surgery, or have locally advanced or distant metastatic, the 6-month progression-free survival rate reached 18.2%, median progression-free survival was 2.7 months, median survival was 10 months, the adverse effects were mild and mainly included fatigue, hypertension and diarrhea. However, it encountered failure in the phase III non-inferiority clinical trial in comparison with sorafenib, its overall survival was not satisfactory.

In summary, no targeted drug is superior to sorafenib in the overall efficacy and safety in treatment of HCC.

1.3. Background of Immunotherapy

Tumor immunotherapy remains a hot spot in the field of tumor therapy for a long time, among which T-cell tumor immunotherapy lies in an essential position. Tumor immunotherapy is to take full advantage of and mobilize cytotoxic T-cell in the body, so as to kill tumors, which may be the most effective and safe way to treat cancer. However, tumor immunotherapy also has a huge obstacle, tumor escape, i.e. tumor cells can inhibit the immune system resulting in unlimited proliferation. There exists an extremely complicated relationship between the tumor immune escape mechanism and the body's immune response to tumor. In the early stage, tumor-specific cytotoxic T-cells are biologically active, but it loses its activity along with tumor growth at late stages. So, tumor immunotherapy is to maximize the patient's own immune response to tumors, not only to activate the original immune system response in the body, but also to maintain a longer and higher immune system response, which is the key in tumor immunotherapy.

Recently, with a deeper understanding of the molecular mechanism of the response to tumor cells, the study on the identification of signaling pathways that limit the antitumor immune response have been further clarified. Programmed cell death protein-1 (PD-1) pathway, one of the most important pathways responsible for the regulation of tumor-induced

immunosuppression, has been confirmed. PD-1 is a protein receptor expressed on the T-cell surface that was discovered in 1992, and be involved in the process of apoptosis. PD-1 belongs to the CD28 family, possessing 23% amino acid homology with cytotoxic T lymphocyte antigen (CTLA) 4, but it mainly expresses on activated T cells, B cells, and myeloid cells, which is different from that of CTLA. PD-1 has two ligands, PD-1 ligand (PD-L) 1 and PD-L2. PD-L1 mainly expresses on T cells, B cells, macrophages, and dendritic cells (DCs), and can be up-regulated in activated cells. Many human solid tumors express PD-L1, which is often associated with poor prognosis . The tumor-infiltrating lymphocytes in cancer patients typically express PD-1, with a damage to their antitumor function. Several antibodies that block PD-1 or PD-L1 have been shown to enhance T-cell function and facilitate tumor cell lysis in preclinical studies.

A number of multinational pharmaceutical companies are developing PD-1 monoclonal antibodies which block the binding of PD-L1 and PD-1, and improve the patient's own immune response to tumors as much as possible, so as to kill tumors . PD-1 monoclonal antibodies developed by BMS and Merck, are currently the most advanced PD-1 antibody drugs. In accordance with the results of the completed pivotal studies, BMS's antibody nivolumab and Merck's antibody pembrolizumab have been approved by FDA for multiple indications.

In July 2014, nivolumab was approved by Japan's Ministry of Health and Welfare for treatment of advanced melanoma, and approved by FDA for treatment of melanoma (December 2014), non-small cell lung cancer (March 2015), renal cell carcinoma (November 2015), and classical Hodgkin's lymphoma (2016) .

Pembrolizumab was approved by FDA for treatment of advanced melanoma (September 2014) and non-small cell lung cancer (October 2015).

Except the above indications, the two companies are conducting large phase III studies for treatment of gastric cancer, bladder cancer, breast cancer, head and neck tumors and lymphoma, and are expected to bring new choices and shocks in the treatment of multiple tumors.

